Bone turnover will be quantified as bone turnover markers (described in section 7.6).

The 0-hypothesis is that low bone turnover does not increase the risk of future fracture in patients with CKD.

This prospective cohort study will provide broad insight into several aspects of CKD-MBD. Other future research questions can be addressed within this cohort study and will therefore provide valuable insight into different aspects of CKD-MBD.

Bone

- 1) Do bone turnover associate with decline in BMD?
- 2) Do bone turnover associate with increased risk of cardiovascular events?

- 3) Do disturbances in the mineral metabolism associate with the presence and progression of osteoporosis (presence of osteoporosis defined as T-score < -2,5 and progression defined as decreasing bone density measured with DEXA-scan)?
- 4) Do vascular derived biomarkers associate with decline in BMD and increased risk of cardiovascular events?
- 5) Does progression of osteoporosis associate with progression of CKD and cardiovascular events?
- 6) Does the bone phenotype and fracture risk differ between patients with and without diabetes?
- 7) Do bone turnover associate with novel circulating CKD-MBD biomarkers including Wnt- and TGF- β -signaling factors?
- 8) Do systemic and urinary markers of acid/base balance (measured as pH in blood and urine) associate with decline in BMD, increased risk of fractures or cardiovascular events?

For detailed description of measure of biomarkers measured in this trial, see section 7.6.

Sarcopenia

Does sarcopenia increase the risk of decline in BMD and future fracture and cardiovascular disease?

- 1) Does sarcopenia associate with low physical activity?
- 2) Does sarcopenia associate with a specific bone phenotype?
- 3) Do systemic and urinary markers of acid/base balance associate with sarcopenia?

Diet

- 1) Does low dietary calcium intake associate with low BMD and decline in BMD?
- 2) Does low dietary phosphate intake associate with low BMD and decline in BMD?
- 3) Does low dietary intake of protein associate with low muscle mass and strength?
- 4) Does a high dietary acid load associate with low muscle mass and strength?
- 5) Does high dietary potassium intake from fruit and vegetables induce hyperkalemia?
- 6) Does low dietary phosphorus intake associate with cardiovascular disease?
- 7) Does sodium intake and urinary sodium excretion associate with the progression of CKD and cardiovascular disease?

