- 8) Does the source of protein (vegetarian versus animal) intake affect albuminuria?
- 9) Does the diet and acid production (pH in urine) associate with the progression of CKD

- 10) Does the source of phosphate (food or additive) affect the urinary excretion?
- 11) Does the balance between the dietary calcium and phosphate intake and the urinary excretion associate with the eGFR?
- 12) Does the product of p-calcium and p-phosphate associate with the eGFR?
- 13) How do the intake of phosphate associate with the intake of calcium

5. Outcomes

Primary outcome

The primary outcome is the difference in time to first fracture between patients with normal bone turnover and low bone turnover based on bone turnover markers at baseline.

Design

This is a prospective cohort study. Patients will be characterized at baseline and reassessed after 3 years. Bone fractures, cardiovascular events, progression of kidney disease, end-stage kidney disease and death will be collected through linkage with registries during follow-up (see section 11). The follow-up will continue until death or end of approvals.

6. Study population

The study will include 1000 patients with chronic kidney disease. The patients will be recruited from the outpatient clinic at the Department of Nephrology at Herlev Hospital.

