7.4 Demographic data, medical history and medication

Date of birth and gender will be registered from medical records. Height and weight will be measured during visits., We will ask participants about ethnic origin/race, alcohol and smoking habits, eating habits, fall within the last 2 years, previous bone fractures, previous treatment with medicine containing steroid, current consumption of vitamin D, calcium, vitamin K, and proton pump inhibitors as well as their height at the age of 18 if this is known. The reason to ask for ethnicity is because of the possible effect on endpoints, we therefore wish to correct for ethnicity in the analysis.

Medical history and present disease are registered. Information of the above will be obtained from the participating subject and from their medical records and it will be recorded at baseline and at 3 years follow-up. Demographic and medical data is collected from medical records to be able to describe the cohort characteristics as it is known that a broad palette of characteristics affects our endpoints of interest. The informed consent from the participant will give investigators direct access to the above mentioned information.

Medication at baseline and at 3 years follow-up are registered.

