7.7 DEXA scan

DEXA scans are performed on all participants at baseline and after 3 years follow-up. The DEXA scan estimates body composition, bone mineral density and vertebral fractures with a whole-body scan.

DEXA provides estimates of three compartments in the body composition: fat mass (FM), fat free mass (FFM), total bone mass (BMC). Appendicular lean mass (ALM) is defined as the sum of lean soft tissue from the arms and legs. Relative ALM is acquired by normalizing ALM to height to account for allometric differences in body size.

The content of calcium in the bones are assessed by the amount of calcium compared to the measured area in g/cm². The scan of the lumbar spine and the hips are performed while the subject is lying down, while the scan of the forearms is performed while sitting. The scan can be performed with clothes on, if the clothes does not contain any metal. The T- and Z-scores are calculated.

Radiation from one DEXA-scan varies from 3 to 30 microsievert.

VFA is a way to assess fractures in columna thoracolumbalis using a DEXA scan. The VFA visualises the different vertebrae, including a possible deformation of the vertebrae. The radiation from one VFA is approximately 3 microsievert.

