7.9 Muscle strength and function

The hand grip strength will be assessed by a JAMAR meter. The muscle function will be evaluated by sit to stand test and 10 m-walk test. The body composition will be measured by bioimpedances. These will be performed at baseline and 3 years follow-up.

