8.2 Case Report Form

An electronic CRF in RedCap is provided, and all data related to this study will be registered in it. This will provide the basis for a central database stored in coded form according to the rules of the

Danish Data Protection Agency. The CRF is to be completed by the study nurse or by the investigator at the time of the subjects visit to the clinic.

9. Statistical evaluation

Analysis of the primary endpoint will be performed after 200 fractures have occurred. The difference in time to first fracture will be analyzed by Cox proportional hazards model. Hazard ratios will be given with 95 % confidence intervals and p-values

Baseline characteristics will be presented with appropriate averages and measures of dispersion according to their distribution.

Continuous outcomes will be presented as graphs of mean and standard error of the mean at each time point. Continuous outcomes with non-normal distribution will be transformed to obtain normality before analysis. For outcomes with a baseline and a single follow-up measurement, comparison between treatment groups will be performed by ANCOVA, with adjustment for the baseline value. Outcomes with baseline and multiple post randomization measurements will be compared as baseline adjusted mean follow-up values using a mixed model repeated measures approach. Categorical outcomes will be compared by Chi²-test. Hypothesis testing will use a 2-sided p-value to confirm or reject the null hypothesis. A p-value less than 0.05 is considered statistically significant.

10. Sample size/power calculation

The incidence of any first fracture is compared between patients with low and non-low turnover as a time to event analyses. The prevalence of low-turnover is expected to be 30%⁹.

An annual incidence of fracture (proximal humerus, forearm, pelvis and hip) of 2 % is expected in the whole cohort²³. To be able to detect a 40 % difference in the incidence of fracture (HR 0.6) in the patients without low turnover bone disease compared to patients with non-low turnover bone disease during 10 years of follow-up, and with a drop out of 20 % a total of 1000 participants will be included ($\beta=0.20$; $\alpha=0.05$). The number of events will be monitored, and the sample size may be adjusted according to the incidence of fractures.

The dietary sub study is an exploratory and descriptive study with 50 participants.

11. End of study

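### The follow-up scan may fall anywhere from 30 to 42 months, and the stated ANCOVA ignores the actual interval, so any systematic timing difference between exposure groups would appear as a difference in BMD decline

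*Protocol*

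**What the plan says.** Section 5 (Design) describes the follow-up as a fixed time point: "Patients will be characterized at baseline and reassessed after 3 years". Table 1 is wider and places V3 at 30 to 42 months after V2, the baseline visit.

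BMD has exactly one follow-up value. Section 7.7 states: "DEXA scans are performed on all participants at baseline and after 3 years follow-up". Section 9 therefore puts it under the rule for a baseline and a single later measurement: "comparison between treatment groups will be performed by ANCOVA, with adjustment for the baseline value".

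Decline in BMD is the outcome of several secondary questions in section 4. Bone 1 asks: "Do bone turnover associate with decline in BMD"; Bone 4, Bone 8 and the main sarcopenia question also use it. The one further adjustment that the protocol names is in section 7.4: "we therefore wish to correct for ethnicity in the analysis". No section uses the actual interval as a covariate, annualises the change or narrows the window.

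**The concern.** Decline accumulates with time. A patient scanned at 42 months has had 40% longer to lose bone than one scanned at 30 months, and the stated model treats both as three-year values.

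The wording of section 9 suits a randomised trial, in which follow-up timing tends to balance between arms. Here the groups are defined by bone turnover, sarcopenia, biomarkers or acid/base status, and nothing in the design balances when they attend. If one exposure group tends to come later, for example because its members are frailer, the model attributes the extra months of loss to the exposure. At stake is the reading of the secondary BMD-decline questions.

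**Working it through.** **Plan figure.** The protocol gives no expected BMD loss, SD of change or detectable BMD difference, so there is nothing to reproduce. The calculation in section 10 concerns fracture only and does not bear on this point.

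**Inputs from the protocol**
- V3 window: 30 to 42 months (Table 1). Ratio of extremes: 42/30 = 1.40.
- Low turnover expected in 30%, total 1000, drop-out 20% (section 10).

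**Assumptions**
- Loss of 0.5–1.5% per year, the same in both groups.
- SD of change 5%.
- Patients with a V3 scan: 1000 × 0.8 = 800, split 240 low turnover and 560 other. The 20% is stated for the 10-year fracture follow-up; attendance at V3 is not given.

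**Standard error of the group difference**

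SE = 5 × √(1/240 + 1/560) = 0.386%.

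**Spurious difference** = annual loss × gap in mean interval (months) / 12

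| Gap in mean interval | At 0.5%/year | At 1.5%/year | In SE units |
|---|---|---|---|
| 0 months | 0 | 0 | 0 |
| 1 month | 0.04% | 0.13% | 0.1–0.3 |
| 3 months | 0.13% | 0.38% | 0.3–1.0 |
| 6 months | 0.25% | 0.75% | 0.6–1.9 |

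**How large a gap is credible?** If visits are spread evenly over the window, the SD of timing is 12/√12 = 3.5 months. A 3-month gap in means is then about 0.9 SD and a 6-month gap about 1.7 SD. Six months would mean, for example, one group averaging 33 months and the other 39. The 1- and 3-month rows are the ones to weigh.

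**Noise when timing is equal.** At 1% per year, evenly spread visits add an SD of 1/√12 = 0.29 points. The total SD becomes √(5² + 0.29²) = 5.008, an increase of under 0.2%.

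**Simulation** (4000 runs, 700 patients split 30/70, loss 1% per year, residual SD 4 points, no true group difference)

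| Gap | Bias, baseline only | Type I error, baseline only | Type I error, interval added |
|---|---|---|---|
| 0 months | 0.00 | 0.05 | 0.05 |
| 1 month | −0.08 | 0.05 | 0.05 |
| 3 months | −0.25 | 0.13 | 0.06 |
| 6 months | −0.50 | 0.32 | 0.05 |

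With the interval in the model, the bias was about zero in every row. At 2% per year and a 3-month gap, the baseline-only type I error was 0.34, against about 0.05 with the interval added.

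**The case against.** The strongest reply is that covariates for secondary outcomes are usually settled in a statistical analysis plan, which is not shown here. Section 9 names an adjustment without saying that it is the only one, and section 7.4 adds ethnicity. This stands in part: section 9 is not a closed covariate list, and a later plan could include the interval. But section 9 does state a model for these outcomes, and that model as written gives no protection against unequal timing.

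Three stronger readings are tempting, and the documents do not support them.

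- **That the wide window in itself distorts the group comparisons.** Unequal intervals do enter each patient's observed decline, but the group contrast is biased only if mean timing differs by exposure. The protocol contains no evidence that it will; later attendance by frailer patients is conjecture.
- **That muscle decline is affected too.** Muscle tests are repeated ("These will be performed at baseline and 3 years follow-up"), but section 4 asks about level, as in "Does low dietary intake of protein associate with low muscle mass and strength", or treats sarcopenia as the exposure. No stated question concerns loss of muscle.
- **That all diet questions on BMD are exposed to the same degree.** Diet 1 and 2 rely largely on calcium and phosphate intake assessed in detail in only 50 patients (section 7.8), in a sub-study that section 10 presents as exploratory. With an illustrative 15/35 split, SE = 5 × √(1/15 + 1/35) = 1.54%, so even the largest 3-month bias is 0.38/1.54 = 0.2 SE.

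**Conclusion.** The point holds in conditional form. The window is a year wide, the groups are not randomised, and the stated ANCOVA does not use the interval, so a systematic difference in V3 timing would pass into the estimated difference in BMD decline. Under the assumed loss rates and SD, the effect is negligible at a 1-month gap and reaches at most about one SE at 3 months. With equal mean timing it is zero.

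A reader might infer that the main result is at risk. It is not: time to first fracture is analysed by a Cox model on registry follow-up and does not depend on when V3 takes place. This is a low-priority improvement to secondary analyses, and its size rests on loss rates, an SD and V3 numbers that the protocol does not supply.

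**What to change.** Add a sentence to section 9: in the ANCOVA of BMD and other V3 outcomes, the time in days from V2 to V3 is included as a covariate alongside the baseline value, and the mean interval is reported by exposure group. A covariate is preferable to annualising the change because it keeps the ANCOVA form already chosen.

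The cost is one degree of freedom and no new data. Visit dates are presumed to be in the electronic CRF, since section 8.2 has it completed at the visit, but the protocol does not say so outright. Precision is unaffected when timing is balanced. In the simulation with a 3-month gap, the SD of the estimate rose from 0.335 to 0.380 (0.380/0.335 = 1.13), which is the price of removing the bias. Fixing the rule before V3 data exist avoids a post-hoc choice.

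### Section 9 allows a p-value to confirm the null hypothesis, so its wording permits a claim of no increased fracture risk whenever p is 0.05 or more

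*Protocol*

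**What the plan says.** Three places in the protocol bear on this.

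- Section 4 (Research questions) states the null for the primary question: "The 0-hypothesis is that low bone turnover does not increase the risk of future fracture in patients with CKD".
- Section 9 (Statistical evaluation) specifies a Cox model for time to first fracture, run once 200 fractures have occurred, with hazard ratios, 95% confidence intervals and p-values. Its closing lines, which cover hypothesis testing in general, say "Hypothesis testing will use a 2-sided p-value to confirm or reject the null hypothesis" and then "A p-value less than 0.05 is considered statistically significant".
- Section 10 (Sample size) bases the study on detecting a difference: HR 0.6, 30% of patients with low turnover, 2% annual fracture incidence, 10 years of follow-up, 20% drop-out, 80% power and alpha 0.05. It gives no margin within which the groups would be regarded as having the same fracture risk.

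Section 16 (Publication) lists inconclusive results as a kind of result separate from negative and neutral ones.

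**The concern.** A test against a null of no increase can reject that null or fail to reject it. Failure to reject may mean that there is no increase, or that the data were too few to show one, and the p-value does not tell these apart. Section 9 names only two outcomes, and one of them is confirmation. With the null of section 4 put in, any p-value of 0.05 or more can be written up as showing that low turnover does not raise fracture risk.

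This bears on the primary question. Section 3 says that disturbed turnover is regarded as harmful to bone strength, and that no study has examined whether it raises fracture risk. A lack of precision stated as an absence of risk would therefore be a consequential error.

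**Working it through.** **Inputs.** HR 0.6, 30/70 split, 2% per year, 10 years, 20% drop-out and 80% power come from section 10. The two-sided 0.05 level and the 200 fractures come from section 9. I read HR 0.6 as non-low against low turnover, so low against non-low is 1/0.6 = 1.67. I treat the 200 fractures as first fractures.

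**1. The plan's own figure.**
- Events needed (Schoenfeld): (1.960 + 0.842)² / [0.3 × 0.7 × (ln 0.6)²] = 7.849 / (0.21 × 0.2609) = 143.2, so 144.
- Ten-year risk: 1 − exp(−0.02 × 10) = 0.1813.
- Patients: 144 / 0.1813 = 795 after rounding up. With drop-out, 795 / 0.8 = 994.

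This reproduces the stated 1000. The calculation is for detecting a difference, and nothing in it supports a conclusion of no difference.

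**2. Precision at the planned analysis.**
- SE(log HR) = 1 / √(200 × 0.3 × 0.7) = 1 / √42 = 0.154.
- 95% CI factor = exp(1.96 × 0.154) = 1.353, so an observed HR above 1 needs to exceed about 1.35 to be significant.

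| Observed HR (low v non-low) | 95% CI | Significant? | Contains 1.67? |
|---|---|---|---|
| 1.00 | 0.74 to 1.35 | No | No |
| 1.20 | 0.89 to 1.62 | No | No |
| 1.30 | 0.96 to 1.76 | No | Yes |

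An observed HR of 1.30 has z = ln 1.30 / 0.154 = 1.70, two-sided p about 0.09. Taken literally, section 9 would count this as confirming no increase, although the interval includes the effect the study was designed to find.

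**3. How often a real increase gives a non-significant result.** P(non-significant) = 1 − Φ(ln HR / SE − 1.96).

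| True HR | 200 events |
|---|---|
| 1.25 | 70% |
| 1.4 | 1 − Φ(2.18 − 1.96) = 41% |
| 1.43 (1/0.7) | 36% |
| 1.67 (1/0.6) | 9% |

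**4. Sensitivity to the event count.** With 20% drop-out, section 10's inputs give 1000 × 0.8 × 0.1813 = 145 fractures at ten years. SE is then 0.181 and the CI factor 1.43. An observed HR of 1.30 has a CI of 0.91 to 1.85, and the miss rates are 54% at a true HR of 1.4 and 20% at 1.67. The 200-event figures are the relevant ones, because section 9 ties the analysis to that count.

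**The case against.** Several objections have force.

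- **A reader might infer that an inconclusive result will be reported as proof of no harm.** The documents do not say so. Section 9 requires the HR with its 95% CI, which shows the imprecision, and section 16 expects some results to be inconclusive. This stands: the wording permits the misreading but does not prescribe it. Still, no sentence assigns the interpretation to the interval, and section 16 does not say when a result counts as inconclusive.
- **The sentence is generic.** It follows the text on ANCOVA, mixed models and chi-square tests, while the Cox analysis has its own paragraph. That is true, but a general statement on hypothesis testing also covers the primary test, and it extends to the many secondary questions, for which no power is stated.
- **The miss rates are ordinary type II error.** They would be the same under correct wording, and the 20% at about 145 events is simply the declared beta. This stands. The rates show why non-significance cannot confirm the null; they do not measure damage done by one verb, and they do not show that the study is too small.
- **A reader might link the point to the background's account of low turnover as a feared condition.** Section 3 ties that fear to vascular calcification, not to fracture, so it does not show that a null fracture result would be used as reassurance.
- **Rules for interpreting a null result may sit in a statistical analysis plan.** They may, and their absence from the protocol is not the point. The point is that the protocol states the logic of the test wrongly.

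**Conclusion.** The wording is wrong and should be corrected, but it is a minor error. Read with section 4, section 9 permits a conclusion of no increased fracture risk from any p-value of 0.05 or more, in a design sized only to detect a difference. At 200 fractures an observed HR of 1.30 would qualify, with a CI up to about 1.76, and a true HR of 1.4 would be non-significant about 41% of the time.

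The figures assume a 30/70 split, proportional hazards, no covariate adjustment and 200 first fractures; with fewer first fractures the intervals widen, as the 145-event figures show. The stated sample size reproduces, and nothing here affects it, alpha, the endpoint or the Cox model.

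**What to change.** In section 9, replace the words that let the p-value confirm the null. Suggested text: *Each null hypothesis will be rejected or not rejected at the two-sided 5% level. A non-significant result will be interpreted from the hazard ratio (or other effect estimate) and its 95% confidence interval, and will not be taken as evidence of no increase in risk.*

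Do not use 1.67 as a margin for absence of effect. It is the effect to detect, and at 200 fractures an observed HR of 1.20 (CI about 0.89 to 1.62) would exclude it while remaining compatible with an increase of about 60%. Any claim of no increase would need its own justified margin, fixed in advance.

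The cost is one or two sentences, with no patients, data or change of analysis. It is best made before results are known.

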14.1 Screening

The study will be streamlined and integrated as much as possible into the usual care to reduce the burden on the participants and study staff.

We expect to screen 1500 patients to be able to include 1000 participants in our study. See section 7.1 for information given to the researchers before consent.

14.2 Risk and discomfort for the patient

Blood samples will be drawn using standard sterile technique in a peripheral vein. The potential risks and discomforts in association to this is pain, hematoma, rarely an infection. A total of approximately 124 ml will be drawn over a 3-year period, maximally 62 ml at once. In section 7.6 is described specific analyses made on blood samples. There will be taken the same amount of blood as in the clinic (20 ml per visit) added with 42 ml to biobanks. As comparison, a blood donor donates 500 ml of blood at a time. The subjects undergo DEXA scans and VFA of column 2 times. The known risk for the patient in relation to these scanning techniques is radiation. The radiation dose from one DEXA scan varies from 3-30 μ Sv, corresponding to <2 weeks of background radiation.

15. Financing and insurance

